7.9.2 Primary Variable

The primary endpoint is the clinical cure rate on Day 7-14, which is defined as the percentage of patients clinically cured at Day 7 to Day 14.

Clinical cure is defined as the absence of signs and symptoms of VVC in terms of having a CVVS score ≤ 3 .

Each of the following 6 vulvovaginal signs and symptoms will be individually scored using the scoring scale below.

- Vulvovaginal signs: erythema, oedema and excoriation
- Vulvovaginal symptoms: itching, burning and irritation

Scoring scale: each score should be objectively defined:

- 0 = none (absent)
- 1 = mild (slight)
- 2 = moderate (definitely present)

Study ID: CL4

3 = severe (marked, intense)

The CVVS score is the sum of the 6 individual scores. If any of the 6 individual signs and symptoms are missing, then the CVVS score will be considered missing. The last non-missing assessment of CVVS in the interval of Day 7-14 will be used. However, if the patient received rescue medication between the CVVS assessments at Day 7 and 14, CVVS data from Day 7 will be used. The same derivation will be made for secondary and exploratory endpoints made during the same time interval Day 7-14.

In the estimand setting, the primary endpoint will take the following identified intercurrent events into account:

1. Concomitant anti-fungal therapy or other treatments related to VVC due to lack of clinical performance prior to CVVS evaluation used for the primary endpoint definition.
2. Treatment discontinuation due to lack of clinical performance.
3. Rescue medication prior to the CVVS evaluation used for the primary endpoint definition.

Rescue medication prior to the CVVS evaluation used for the primary endpoint definition. From a practical perspective, bullet points 1 and 3 above will be regarded as the same in this study. Applying the composite strategy to account for these intercurrent events, these have been incorporated in the endpoint definition. Thus, to be defined as clinically cured on Day 7-14, the patient needs to have the last available CVVS score equal to or below 3 at Day 7-14, and that none of the above stated intercurrent events have occurred. If the CVVS score is above 3, or any of the intercurrent events has occurred, the patient is defined as not clinically cured on Day 7-14.

Patients with missing CVVS score at Day 7-14 and no intercurrent events will be considered as missing in the analysis.

The primary endpoint clinical cure rate on Day 7-14, as defined in the section will be calculated and presented together with a one-sided 95 % CI based on the Wilson score.

The primary performance objective of the trial is to show that the clinical cure rate is above 30 %, i.e. to show that the lower limit of the one-sided 95 % CI for the observed cure rate is above 30 %.

Hypotheses for the primary clinical performance endpoint

Null hypothesis: Clinical cure rate is less than or equal to 30 %.

Alternative hypothesis (one-sided): Clinical cure rate is above 30 %.

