5.4.3 Day 7 (+2 days); Follow-up visit

Patients will visit the clinic on Day 7 to have gynaecological examination performed. The Investigator or an authorised designee will assess the presence of vulvovaginal signs (erythema, oedema, and excoriation) and symptoms (itching, burning, and irritation) and score each sign and symptom on a scale of 0 to 3 (see [Section 9.1.2](#)).

Vaginal samples will be examined under a microscope for yeast forms (hyphae or pseudohyphae) or budding yeast. Vaginal secretion samples collected by swabs will be used for culture and for sequencing analysis of the vaginal microbiome (this sample will be taken in duplicates). If the patient is menstruating at this timepoint, the visit should be postponed until the menstruation is over, even though the visit will happen outside the visit window.

Procedures to be performed:

- Gynaecological examination by Investigator or authorised designee, evaluating vulvovaginal signs (erythema, oedema, and excoriation) and symptoms (itching, burning, and irritation) according to the scoring scale (0 to 3).
- Fungal saline microscopy assessment
- Vaginal swab for
 - Culture
 - Sequencing
- Vaginal self-swab for:
 - Sequencing
- Vaginal pH
- Recording of
 - Concomitant medications
 - AEs
 - Potential menstruation onset
- Product accountability – patients should be asked to return all used and not used treatment packages

Rescue treatment, according to standard clinical practice, will be offered if the intensity of the VVC symptoms is the same or higher compared to the inclusion visit (Visit 1, Day 0). See details in [Section 7.5.2](#).

An assessment of mycological cure will be done as soon as the results from the laboratory are received. A mycological cure is defined as no presence of *Candida* species. If the patient has both a clinical and mycological cure at Day 7, the Day 14 visit should be cancelled.

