5.4.5 Day 14 (± 2 days); Follow-up visit

Patients with clinically and mycologically cured VVC at Day 7, or patients initiating rescue treatment Day 7 (even if they are clinically cured according to the CIP), will not perform the Day 14-visit. For these patients, this visit will be omitted.

Patients without clinically and mycologically cured VVC at Day 7 will visit the clinic on Day 14 to have gynaecological examination performed. The Investigator or an authorised designee will assess the presence of vulvovaginal signs (erythema, oedema, and excoriation) and symptoms (itching, burning, and irritation) and score each sign and symptom on a scale of 0 to 3 (see [Section 9.1.2](#)).

Vaginal samples will be examined under a microscope for yeast forms (hyphae or pseudohyphae) or budding yeast. Vaginal secretion samples collected by swabs will be used for culture and for sequencing analysis of the vaginal microbiome. If the patient is menstruating at this timepoint, the visit should be postponed until menstruation is over.

The Investigator or delegatee will ask the patient about potential menstruation onset.

Procedures to be performed:

- Gynaecological examination by Investigator or authorised designee, evaluating vulvovaginal signs (erythema, oedema, and excoriation) and symptoms (itching, burning, and irritation) according to the scoring scale (0 to 3).
- Fungal microscopy assessment (KOH or saline preparation)
- Vaginal swab for
 - Culture
 - Sequencing
- Recording of:
 - Concomitant medications
 - AEs
 - Potential menstruation onset

Rescue treatment, according to standard clinical practice, will be offered if the intensity of VVC symptom is the same or higher compared to the inclusion visit (Visit 1, Day 0). See details in [Section 7.5.2](#).

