6.5 Restrictions

During the study, the following medications are not allowed and should be avoided:

1. Anti-fungal medication related to VVC.
2. Other treatments for VVC (e.g. probiotics like Candicur and Multigyn).

Also see further information on rescue medication in [Section 7.5.2](#) and prior and concomitant medications in [Section 8.4](#).

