7.5.2 Rescue medication

On Days 7 and 14, patients having VVC symptoms of the same or higher intensity compared to the inclusion visit (Day 0), will be offered rescue treatment, if considered necessary. For

details on VVC symptom score see [Section 9.1.2](#) Rescue treatment will be according to standard clinical routines, as described below.

Patients will receive a prescription of fluconazole (50-150 mg as a single dose, orally) or Clotrimazole pessary (500 mg as a single dose, intra-vaginally) and if necessary, topical treatment with 1% clotrimazole or 1% clotrimazole/1% hydrocortisone. Rescue medication will not be provided by the Sponsor, however the Sponsor will reimburse the cost.

In addition, patients with recurrence or persistent symptoms on Day 25 (i.e. symptoms recurred on Day 25) may also be offered rescue treatment, according to the standard clinical routines mentioned above. The site will decide whether a visit to the clinic is needed and if rescue medication should be prescribed.

Patients taking rescue medications prior to the visit where clinical cure is assessed (Day 7 or Day 14), will be considered in the statistical analysis as described in [Section 12](#). In general, these patients should stay in the study and continue to be followed-up.

The use of any rescue medication will be recorded in the eCRF.

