12.4.2 Primary endpoint analysis

In the estimand setting, the primary endpoint will, in addition to the definition stated in [Section 4.1.1](#), take the following identified intercurrent events into account:

1. Concomitant anti-fungal therapy or other treatments related to VVC due to lack of clinical performance prior to CVVS evaluation used for the primary endpoint definition.
2. Treatment discontinuation due to lack of clinical performance.
3. Rescue medication prior to the CVVS evaluation used for the primary endpoint definition.

Applying the composite strategy to account for these intercurrent events, these have been incorporated in the endpoint definition. Thus, to be defined as clinically cured on Day 7-14, the patient needs to have the last available CVVS score equal to or below 3 at Day 7-14, and that none of the above stated intercurrent events have occurred. If the CVVS score is above 3, or any of the intercurrent events has occurred, the patient is defined as not clinically cured on Day 7-14.

Patients with missing CVVS score at Day 7-14 and no intercurrent events will be considered as missing in the analysis.

The primary endpoint clinical cure rate on Day 7-14, as defined in the section will be calculated and presented together with a one-sided 95 % CI based on the Wilson score.

The primary performance objective of the trial is to show that the clinical cure rate is above 30 %, i.e. to show that the lower limit of the one-sided 95 % CI for the observed cure rate is above 30 %.

Hypotheses for the primary clinical performance endpoint

Null hypothesis: Clinical cure rate is less than or equal to 30 %.

Alternative hypothesis (one-sided): Clinical cure rate is above 30 %.

Sensitivity analyses to evaluate the effect of missing data for any of the 6 individual vulvovaginal signs and symptoms scores included in the CVVS score will be performed. Details on the sensitivity analyses will be described in the SAP.

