7.2.2 Per Protocol Analysis Set

The per protocol analysis set (PPAS) is defined as the subset of subjects in the full analysis set for whom no protocol deviation judged as having an impact on the primary efficacy analysis was reported or identified.

Statistical Analysis Plan

Study ID: CL4

The decision as to which protocol deviations should be considered as reason for exclusion from the per protocol analysis set should be made at the clean file meeting and documented in the clean file report.

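### Day 25 mycological cure and Day 25 symptom endpoints have no rescue rule; as a minor point, CIP and SAP classify one rare rescue sequence differently for the primary endpoint

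*SAP*

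**What the plan says.** **Day 25.** CIP 12.4.3.2 and SAP 7.9.3 give the same definitions. Continued clinical response needs clinical cure at Day 7-14, no reported recurrence, and no rescue up to Day 25. Day 25 mycological cure is defined by culture alone. Day 25 symptom reduction and the Day 25 change in the symptom sum are defined by the questionnaire scores alone.

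Rescue is part of the plan. CIP 7.5.2 offers it at Days 7 and 14 to women whose symptoms are at least as intense as on Day 0, and says that women who take it should in general remain in follow-up. CIP 5.4.6 asks all patients for a questionnaire and a self-swab at Day 25.

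**Day 7-14.** SAP 7.9.2 uses the last non-missing CVVS in the interval, with one exception: "However, if the patient received rescue medication between the CVVS assessments at Day 7 and 14, CVVS data from Day 7 will be used". It extends this derivation to secondary and exploratory endpoints in the Day 7-14 interval, and no further.

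CIP 12.4.2 has no such exception. It decides on the last available score and adds: "If the CVVS score is above 3, or any of the intercurrent events has occurred, the patient is defined as not clinically cured". The events are rescue before the score used, other VVC treatment before that score if taken because the device was not working, and stopping treatment for that reason. On the first two, the SAP remarks: "From a practical perspective, bullet points 1 and 3 above will be regarded as the same in this study". SAP 6.2.2 plans a review of concomitant medication before database lock to decide what counts as an intercurrent event. SAP 7.10 lists five changes from the CIP; the Day 7 exception is not among them.

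**The concern.** There is no control arm, so nothing in the data separates the effect of rescue from that of the pessary. A woman rescued under the stated rule had, at that visit, symptoms no better than at baseline. If an antifungal then clears her culture or eases her symptoms by Day 25, she counts as a mycological cure or a symptom responder in the main (FAS) analysis. The plan recognises this problem for continued response and guards against it there, but not for the neighbouring Day 25 endpoints.

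The minor issue is of a different kind. The primary endpoint has two written definitions that part company for one sequence of events, and with 26 women the pass mark can turn on a single classification.

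**Working it through.** **A. Day 25 endpoints**

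1. Which rule could cover rescue at Day 25?
   - The Day 7 substitution in SAP 7.9.2 is limited to Day 7-14.
   - The composite strategy in SAP 7.9.1 works only through the endpoint definitions, and these three definitions contain no rescue term.
   - PPAS25 (SAP 7.2.3) removes women with protocol deviations judged relevant to Day 25. Planned rescue is not a deviation, and the set is supportive only.

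   No rule covers rescue in the FAS.
2. Size. Each rescued woman counted as a responder adds at most 1/26 = 3.8 points. The documents give no number of rescued women. For an assumed 0, 1, 2, 3 or 4 the ceiling is 0, 3.8, 7.7, 11.5 or 15.4 points.
3. Illustration with an assumed 10 responders without rescue and 3 after it: 10/26 = 38.5% (two-sided 95% Wilson 22.4 to 57.5) becomes 13/26 = 50.0% (32.1 to 67.9). This is an upper bound, since some of the three might have improved anyway.

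**B. Primary endpoint**

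1. The plan's own figure. With a null of 30%, an assumed rate of 54%, one-sided 5% and 80% power (CIP 12.6), n = [(1.6449·√(0.30·0.70) + 0.8416·√(0.54·0.46))/0.24]² = 23.90, so 24. This agrees with the plan; 26 are enrolled.
2. Take rescue, or a VVC treatment classified as an intercurrent event at the SAP 6.2.2 review, falling between two obtained scores:

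| Day 7 CVVS | Day 14 CVVS | CIP 12.4.2 | SAP 7.9.2 |
|---|---|---|---|
| ≤3 | ≤3 | not cured | cured |
| ≤3 | >3 | not cured | cured |
| >3 | ≤3 | not cured | not cured |
| >3 | >3 | not cured | not cured |

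Under the CIP the treatment precedes the score used, so it is an intercurrent event. Under the SAP the score used moves back to Day 7, so the treatment comes after it. (SAP 7.9.2 also repeats the last-available-score sentence; the table takes the explicit exception as governing.)

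3. Who can reach the first two rows? CIP 5.4.3 says: "If the patient has both a clinical and mycological cure at Day 7, the Day 14 visit should be cancelled". A woman who is clinically cured but still culture positive therefore returns on Day 14. But CIP 5.4.5 says that "patients initiating rescue treatment Day 7 (even if they are clinically cured according to the CIP), will not perform the Day 14-visit", so rescue begun at the Day 7 visit does not normally lead there. What remains is treatment between visits, and CIP 6.5 introduces VVC antifungals and other VVC treatments with "During the study, the following medications are not allowed and should be avoided".
4. Pass mark. The one-sided Wilson lower limit is L = [p + z²/2n − z·√(p(1−p)/n + z²/4n²)]/(1 + z²/n), with z = 1.645. For 12/26, L = 31.2% (pass); for 11/26, L = 27.8% (fail). With 24 evaluable, 11/24 gives 30.4% and 10/24 gives 26.8%.
5. Chance that the two definitions give different verdicts. Let p be the true cure rate under the CIP and q the per-woman chance of the sequence. It is P(X≥12 | 26, p+q) − P(X≥12 | 26, p). For q = 1% or 2% (assumed; 0.26 or 0.52 women expected):
   - p = 30%: 7.5 − 6.0 = 1.5 or 9.3 − 6.0 = 3.3 points
   - p = 41% (the CL1 rate): 40.5 − 36.5 = 4.0 or 44.6 − 36.5 = 8.1 points
   - p = 54%: 86.5 − 84.1 = 2.4 or 88.6 − 84.1 = 4.5 points

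   With q = 0 there is no difference. The 6.0% at p = 30% comes from the discreteness of the Wilson rule, not from this issue.

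**The case against.** **On Day 25.** The two documents agree with each other here. The endpoints are descriptive and have no pass mark. Continued response already gives a Day 25 measure free of rescue. Counting rescued women as failures rather than reporting what was observed is a choice of estimand, and the numbers of rescued women used above are assumed. All of this stands, and it keeps the point modest. It does not close the gap: as written, the reported Day 25 rates mix device and rescue effects without showing how much.

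**On the primary endpoint.** Three stronger readings are tempting, and the documents support none of them.

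- *That the SAP rule lets an antifungal's effect into the primary endpoint.* It does not. The Day 7 score is taken before the treatment, and the later score is set aside.
- *That the CIP makes every woman who takes an antifungal between the visits not cured.* It does so for rescue. Other VVC treatment counts only if taken for lack of clinical performance, and SAP 6.2.2 assigns that judgement to a review before database lock.
- *That women who start rescue at the Day 7 visit are classified differently.* They have no Day 14 visit and are decided on Day 7 in both documents.

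It is also fair to say that the Day 7 rule is written openly in the SAP, and that SAP section 2 asks for a CIP amendment only for principal features. Women who took disallowed treatment might be left out of the PPAS, which keeps those for whom "no protocol deviation judged as having an impact on the primary efficacy analysis was reported or identified", but that set is supportive and its exclusions are settled at the clean file meeting.

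**Conclusion.** The Day 25 gap is real and is the main point. Mycological cure, symptom reduction and symptom change at Day 25 can credit the device with the effect of planned rescue, by at most 3.8 points per woman on each proportion. The total depends on a number of rescued women that the documents do not give. The primary test is not affected.

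The primary-endpoint difference is a minor reconciliation. It is a difference in definition for a sequence that is close to off-protocol and may not occur. It deserves settling because it can only move women from not cured to cured, is not listed in SAP 7.10, and could decide the result at 11 against 12 of 26. The 1% and 2% chances used to size it are assumptions.

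**What to change.** **SAP 7.9.3 (main).**
- Count women with rescue, or another VVC treatment classified as an intercurrent event under SAP 6.2.2, before the Day 25 assessment as not mycologically cured and as having no symptom reduction at Day 25. Time this by the date of the swab or questionnaire itself, since the swab may be postponed for menstruation.
- Report the number of women affected, and the as-observed rates beside these.
- For the continuous Day 25 change, show results with and without post-rescue values.
- In the same edit, say whether the Day 7-14 derivation in 7.9.2 covers the Day 11 and Day 14 symptom sums.

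**SAP 7.9.2 (minor).** Choose one:
- Follow CIP 12.4.2, keeping its restriction of non-rescue treatment to that taken for lack of clinical performance. Acknowledge that women treated shortly after the Day 7 visit are then handled differently from those rescued at it.
- Keep the SAP rule, list it in 7.10 (with a CIP amendment if it is judged a principal feature), and report the primary endpoint under both classifications.

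**Cost.** A few lines of text. Rescue and concomitant medication are already recorded in the eCRF. Day 25 rates may be slightly lower. The change concerns the analysis only, not who is offered rescue.

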6.2.1 Rescue medication

On Days 7 and 14, patients having VVC symptoms of the same or higher intensity compared to the inclusion visit (Day 0), will be offered rescue treatment, if considered necessary. Rescue treatment will be according to standard clinical routines, as described below. Any rescue treatment will be administered after all assessments have been completed during the visit.

Patients will receive a prescription of fluconazole (50 mg as a single dose, orally) or clotrimazole pessary (500 mg as a single dose, intra-vaginally) and if necessary, topical treatment with 1% clotrimazole or 1% clotrimazole/1% hydrocortisone.

In addition, patients with recurrence or persistent symptoms on Day 25 (i.e., symptoms recurred on Day 25) may also be offered rescue treatment, according to the standard clinical routines mentioned above. The site will decide whether a visit to the clinic is needed and if rescue medication should be prescribed.

Patients taking rescue medications prior to the visit where clinical cure is assessed (Day 7 or Day 14), will be considered in the statistical analysis as described in Section 7.9.1.

The use of any rescue medication will be recorded in the eCRF.

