6.2.2 Restrictions

During the study, the following medications are not allowed and should be avoided:

1. Anti-fungal medication related to VVC – explicitly anatomical therapeutic chemical (ATC) codes J02A and D01AC.
2. Other treatments for VVC (e.g. probiotics like Candicur and Multigyn).

Since use of concomitant anti-fungal therapy or other treatments related to VVC due to lack of efficacy prior to CVVS evaluation used for the primary endpoint definition is considered an intercurrent event, a review of all concomitant medication will be performed prior to data base lock to classify the concomitant medication as an intercurrent event or not.

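### SAP 7.9.2's return to the Day 7 score, read literally, counts as cured a woman rescued between Day 7 and a Day 14 CVVS whom the protocol counts as not cured

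*SAP*

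**What the plan says.** **Protocol 12.4.2.** To be cured, "the patient needs to have the last available CVVS score equal to or below 3 at Day 7-14", and none of three intercurrent events may have occurred. Event 3 is "Rescue medication prior to the CVVS evaluation used for the primary endpoint definition". Event 1 is other anti-fungal or VVC treatment taken for lack of clinical performance before the same evaluation. Any event makes the woman not cured. The section has no return to an earlier score.

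**SAP 7.9.2.** It repeats the cure definition and the three events, but first adds that "if the patient received rescue medication between the CVVS assessments at Day 7 and 14, CVVS data from Day 7 will be used". It then says: "The same derivation will be made for secondary and exploratory endpoints made during the same time interval Day 7-14". It also says: "From a practical perspective, bullet points 1 and 3 above will be regarded as the same in this study".

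**Rescue and visits.** Protocol 7.5.2 offers rescue on Days 7 and 14 only when symptoms are at least as intense as on Day 0. SAP 6.2.1 adds: "Any rescue treatment will be administered after all assessments have been completed during the visit". Under Protocol 5.4.5, women who start rescue at Day 7 omit the Day 14 visit, as do women with both clinical and mycological cure. Women with clinical cure but a positive culture should attend Day 14.

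**Declared changes.** SAP 7.10 lists five changes to the planned analysis. The Day 7 fallback is not among them.

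**The concern.** Both documents declare a composite strategy: needing rescue before the deciding score is itself a failure. The SAP clause changes which score decides, and the event is defined relative to that score. Moving the score back to Day 7 therefore also removes the event. Read literally, a woman at 3 or less on Day 7 who relapses untreated by Day 14 fails, while one who relapses and takes rescue before her Day 14 visit passes.

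The primary test rests on about 24 to 26 binary outcomes against a fixed 30% bound, so one reclassified woman can change the result. The other safeguards do not reach this case:

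- The pre-lock medication review in SAP 6.2.2 applies the same test: therapy "prior to CVVS evaluation used for the primary endpoint definition is considered an intercurrent event".
- The per-protocol analysis is only supportive.
- The requirement of no rescue up to Day 25 belongs to the Day 25 endpoint alone.

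**Working it through.** **1. The two rules side by side.** Rescue here means rescue after the Day 7 assessment and, where there is a Day 14 CVVS, before it.

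| Day 7 CVVS | Rescue | Day 14 CVVS | Protocol 12.4.2 | SAP 7.9.2, literal |
|---|---|---|---|---|
| ≤ 3 | yes | present | Day 14 is scored, rescue precedes it: not cured | Day 7 is scored, rescue follows it: cured |
| > 3 | yes | present | not cured | not cured |
| ≤ 3 | yes | absent (5.4.5) | Day 7 is scored: cured | Day 7 is scored: cured |
| ≤ 3 | no | > 3 | not cured | not cured |

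Only the first row differs, and there the SAP adds a cure. Relative to the protocol the clause can raise the cure rate but never lower it.

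**2. What is left of event 3 under the SAP.** Planned rescue is given after the visit's assessments, so none precedes the Day 7 score. Rescue between the two assessments moves the score back to Day 7. Event 3 then applies only to rescue before the Day 7 assessment, or before Day 14 when there is no Day 7 CVVS.

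**3. How a woman enters the first row.** A CVVS of 3 or less at Day 7 means a symptom sum of 3 or less that day. An offer of rescue needs that sum to be at or above Day 0, so her Day 0 symptom sum was also 3 or less. Inclusion allows this, for example with one moderate symptom and one moderate sign. She must then also have a Day 14 CVVS. The routes are a Day 7 prescription taken late, a Day 14 visit held despite Day 7 rescue, or treatment between visits.

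**4. The plan's own sample size.** Inputs from Protocol 12.6: null rate 0.30, assumed rate 0.54, one-sided 5%, 80% power.

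n = [(1.645·√(0.30·0.70) + 0.842·√(0.54·0.46)) / 0.24]² = 23.9, so 24. The stated figure is reproduced.

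**5. The pass mark.** One-sided 95% Wilson lower limit, with z = 1.645 and p = x/n:

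L = [p + z²/(2n) − z·√(p(1−p)/n + z²/(4n²))] / (1 + z²/n)

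- 12/26: (0.5136 − 0.1690)/1.1041 = 31.2%, pass
- 11/26: (0.4751 − 0.1676)/1.1041 = 27.8%, fail
- 11/24: 30.4%, pass
- 10/24: 26.8%, fail

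**6. Chance that the rules disagree, given one affected woman.** This is an assumption, since the documents give no count. Let X be the cures among the other women, binomial with rate p. The protocol counts X cures and the SAP counts X + 1. They disagree only when X is one below the pass mark: X = 11 of 25 when 26 are evaluable, or X = 10 of 23 when 24 are.

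| True rate in the others | Disagree, n = 26 | Pass under protocol / SAP, n = 26 | Disagree, n = 24 |
|---|---|---|---|
| 30% (null) | 5.4% | 4.4% / 9.8% | 6.5% |
| 41% (CL1) | 15.2% | 30.3% / 45.5% | 16.1% |
| 54% (planning) | 9.6% | 78.9% / 88.6% | 10.0% |

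With no affected woman the difference is zero.

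**The case against.** **The group is nearly empty by design.** This stands. Women who start rescue at Day 7 skip Day 14, the offer rule rarely coincides with a score of 3 or less, and self-treatment is barred. The figures in step 6 are conditional. If the chance of having one such woman were 10% (an assumption), the rules would disagree in roughly 0.5% to 1.6% of trials. One outcome deciding at the threshold is also true of any binary test this small. Still, the SAP has a clause for this very situation, and women with clinical cure but a positive culture are due back on Day 14. Of the culture, Protocol 5.4.3 says: "An assessment of mycological cure will be done as soon as the results from the laboratory are received". That leaves an interval in which treatment could start.

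**The SAP never says these women are cured.** Correct. The outcome follows from the event being tied to the score used. The SAP still asks for the last available score and still makes any event a failure, so two programmers could code the case differently. Unclear wording explains this as well as intent does.

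**The fallback harmonises attenders and non-attenders.** This has force. Of two women rescued after a Day 7 score of 3 or less, the one who skips Day 14 is cured under both documents. Restoring the protocol rule fails only the one who attends. The sensitivity analysis in the fix addresses this.

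**The clause is written openly in 7.9.2, and the protocol leaves detail to the SAP.** True, but it alters who counts as cured on the primary endpoint. SAP section 2 asks for a protocol amendment when principal features change.

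**Conclusion.** The conflict is in the text, but narrow. It concerns only women with a Day 7 CVVS of 3 or less, rescue after that assessment and a Day 14 CVVS. For them the protocol gives not cured and the SAP read literally gives cured. The difference runs one way, leaves event 3 almost without effect, and is not in SAP 7.10. The size is zero if no such woman exists. If exactly one exists among 26 evaluable women, the trial conclusion differs with probability 5.4% to 15.2% over the three rates considered.

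A reader might infer more than the documents support:

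- *That every woman rescued at Day 7 is scored differently.* She is not: without a Day 14 visit both documents use Day 7, and Protocol 5.4.5 foresees such a woman being clinically cured.
- *That any VVC therapy between visits is covered.* Event 1 requires lack of clinical performance as the reason. Treatment prompted only by a late positive culture does not clearly qualify, even though the SAP merges events 1 and 3.
- *That the clause was added knowing the results.* SAP version 2.0 was signed on 25 March 2024, after the planned last visit in 2023, but the documents do not say when the clause was written or what was then known.

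**What to change.** In SAP 7.9.2:

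- Limit the Day 7 fallback to the secondary and exploratory scores.
- State that for the primary endpoint, rescue, or VVC therapy for lack of clinical performance, taken after the Day 7 assessment and before a Day 14 CVVS means not cured, as in Protocol 12.4.2.
- Leave rescue given after the scored Day 14 CVVS as it is; the documents agree there.

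In SAP 7.10, list the clause.

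Add one sensitivity analysis of the primary endpoint. It counts as not cured every woman with rescue after the Day 7 assessment and before the Day 14 assessment, or before the end of the Day 14 window if that visit was not held. Classification then no longer depends on Day 14 attendance.

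If outcomes are already known, report the primary result under both rules.

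The cost is one or two sentences in 7.9.2, a line in 7.10, one derivation and one extra table. Rescue and concomitant medication are already recorded in the eCRF, so no visits or data are added. The downside is a slightly lower cure rate if any such woman exists.
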